4. CASE DEFINITION

Table 5 Case definition of *P. falciparum* infection

Case definition	Asexual blood stage P. falciparum parasite density > 0 detected by blood slide reading.
------------------------	--

5. STUDY COHORT

5.1. Number of subjects/centers

The target is to enroll approximately 150 subjects (26 subjects per vaccine group and between 20 and 30 subjects in the infectivity control group) aged 18 to 55 years at the time of first vaccination. Refer to Section 11.4 for the determination of sample size.

Overview of the recruitment plan

Recruitment will be conducted using multiple methods such as advertisements, flyers, posters, word of mouth and other institutional review board (IRB) approved methods. There will be an opportunity for subjects who enroll in the study to receive compensation for recruitment of additional subjects.

Recruitment for the vaccine groups will be terminated when 26 subjects per vaccine group have been enrolled (i.e. informed consent form signed), eligible per screening and inclusion/exclusion criteria and available on the day of first vaccination.

Recruitment for infectivity control group will be terminated when a maximum of 30 subjects have been enrolled (i.e. informed consent form signed), eligible per screening and inclusion/exclusion criteria, and available on the day of challenge. For infectivity control group **only**, in the rare event that malaria-naïve volunteers cannot be recruited, subjects may be enrolled if they have not been diagnosed with malaria (clinical disease or parasitemia) within the last five years (inclusive).

5.2. Inclusion criteria for enrolment

Deviations from inclusion criteria are not allowed because they can potentially jeopardize the scientific integrity of the study, regulatory acceptability or subject safety. Therefore, adherence to the criteria as specified in the protocol is essential.

All subjects must satisfy ALL the following criteria at study entry:

- Subjects who, in the opinion of the investigator, can and will comply with the requirements of the protocol (e.g. completion of the diary cards, return for follow-up visits).
- Written informed consent obtained from the subject prior to performing of any study specific procedure.
- A male or female between, and including, 18 and 55 years of age at the time of enrolment.
- Healthy subjects as established by medical history and clinical examination before entering into the study.

- Available to participate for the duration of the study (approximately 16 months per vaccinated subject and approximately three months per subject in the infectivity control group).
- Female subjects of non-childbearing potential may be enrolled in the study.
 - Non-childbearing potential is defined as pre-menarche, current tubal ligation, hysterectomy, ovariectomy or post-menopause.

Please refer to the [glossary of terms](#) for the definition of menarche and menopause.

- Female subjects of childbearing potential may be enrolled in the study, if the subject:
 - has practiced adequate contraception for 30 days prior to vaccination, and
 - has a negative pregnancy test at enrolment, and
 - has agreed to continue adequate contraception during the entire treatment period and for two months after completion of the vaccination series and/or malaria challenge.

Please refer to the [glossary of terms](#) for the definition of adequate contraception.

5.3. Exclusion criteria for enrolment

Deviations from exclusion criteria are not allowed because they can potentially jeopardize the scientific integrity of the study, regulatory acceptability or subject safety. Therefore, adherence to the criteria as specified in the protocol is essential.

The following criteria should be checked at the time of study entry. If ANY exclusion criterion applies, the subject must not be included in the study:

- Use of any investigational or non-registered product (drug or vaccine) other than the study vaccines during the period starting 30 days before the first dose of study vaccines (Day -29 to Day 0), or planned use during the study period.
- Any medical condition that in the judgment of the investigator would make intramuscular (IM) injection unsafe.
- Chronic administration (defined as more than 14 days in total) of immunosuppressants or other immune-modifying drugs during the period starting six months prior to the first vaccine dose. For corticosteroids, this will mean prednisone ≥ 20 mg/day (for adult subjects), or equivalent. Inhaled and topical steroids are allowed.
- Administration of long-acting immune-modifying drugs at any time during the study period (e.g. infliximab).
- Chronic use of antibiotics with antimalarial effects (e.g. tetracyclines for dermatologic patients, sulfa for recurrent urinary tract infections, etc.).
- Planned administration/administration of a vaccine not foreseen by the study protocol in the period starting seven days before the first dose.

- Concurrently participating in another clinical study, at any time during the study period, in which the subject has been or will be exposed to an investigational or a non-investigational vaccine/product (pharmaceutical product or device).
- Seropositive for HBsAg or HCV.
- Documented HIV-positive subject.
- Previous vaccination against malaria.
- History of malaria chemoprophylaxis within 60 days prior to vaccination.
- Any history of malaria (for the vaccine groups).
- Planned travel to malaria endemic areas during the study period.
- History of splenectomy.
- Any confirmed or suspected immunosuppressive or immunodeficient condition, based on medical history and physical examination.
- Family history of congenital or hereditary immunodeficiency.
- History of any reaction or hypersensitivity likely to be exacerbated by any component of the vaccine.
- History of anaphylaxis post-vaccination.
- Hypersensitivity to latex.
- History of any reaction or hypersensitivity likely to be exacerbated by chloroquine.
- History of psoriasis and porphyria, which may be exacerbated after chloroquine treatment.
- Current use of medications known to cause drug reactions to chloroquine.
- History of severe reactions to mosquito bites.
- Major congenital defects.
- Serious chronic illness.
- History of any neurological disorders or seizures (except for a single episode of simple febrile seizure in childhood).
- Acute disease and/or fever at the time of enrolment.
 - Fever is defined as temperature $\geq 37.5^{\circ}\text{C}/99.5^{\circ}\text{F}$ for oral, axillary or tympanic route, or $\geq 38.0^{\circ}\text{C}/100.4^{\circ}\text{F}$ for rectal route.
 - Subjects with a minor illness (such as mild diarrhea, mild upper respiratory infection) without fever may be enrolled at the discretion of the investigator.
- Acute or chronic, clinically significant pulmonary, cardiovascular, hepatic or renal functional abnormality, as determined by physical examination or laboratory screening tests.

- Any abnormal baseline laboratory screening tests: ALT, AST, creatinine, hemoglobin, platelet count, total WBC, out of normal range as defined in the protocol.
- Evidence of increased cardiovascular disease risk, "moderate" or "high", according to the National health and nutrition examination survey I (NHANES I) criteria.

Note: NHANES I criteria will be applied for all subjects including subjects aged 18-35 years old (see [APPENDIX C](#)).

- An abnormal baseline screening electrocardiogram, defined as one showing pathologic Q waves and significant ST-T wave changes; left ventricular hypertrophy; any non-sinus rhythm excluding isolated premature atrial contractions; right or left bundle branch block; or advanced (secondary or tertiary) A-V heart block.
- Hepatomegaly, right upper quadrant abdominal pain or tenderness.
- Personal history of autoimmune disease.
- Administration of immunoglobulins and/or any blood products during the period starting three months before the first dose of study vaccine or planned administration during the study period.
- Pregnant or lactating female.
- History of chronic alcohol consumption and/or drug abuse.
- Female planning to become pregnant or planning to discontinue contraceptive precautions.
- History of blood donation within 56 days preceding enrolment.
- Any other significant finding that in the opinion of the investigator would increase the risk of having an adverse outcome from participating in this study.

6. CONDUCT OF THE STUDY

6.1. Regulatory and ethical considerations, including the informed consent process

The study will be conducted in accordance with all applicable regulatory requirements.

The study will be conducted in accordance with the ICH Guideline for Good Clinical Practice (GCP), all applicable subject privacy requirements and the guiding principles of the Declaration of Helsinki.

GSK will obtain favorable opinion/approval to conduct the study from the appropriate regulatory agency, in accordance with applicable regulatory requirements, prior to a site initiating the study in that country.

Conduct of the study includes, but is not limited to, the following:

- IRB/Independent Ethics Committee (IEC) review and favorable opinion/approval of study protocol and any subsequent amendments.
- Subject informed consent.
- Investigator reporting requirements as stated in the protocol.

GSK will provide full details of the above procedures to the investigator, either verbally, in writing, or both.

Freely given and written or witnessed/ thumb printed informed consent must be obtained from each subject, as appropriate, prior to participation in the study.

GSK Biologicals will prepare a model Informed Consent Form (ICF) which will embody the ICH GCP and GSK Biologicals required elements. While it is strongly recommended that this model ICF is to be followed as closely as possible, the informed consent requirements given in this document are not intended to pre-empt any local regulations which require additional information to be disclosed for informed consent to be legally effective. Clinical judgment, local regulations and requirements should guide the final structure and content of the local version of the ICF.

The investigator has the final responsibility for the final presentation of the ICF, respecting the mandatory requirements of local regulations. The ICF generated by the investigator with the assistance of the sponsor's representative must be acceptable to GSK Biologicals and be approved (along with the protocol, and any other necessary documentation) by the IRB/IEC.

6.2. Subject identification and randomization of treatment

6.2.1. Subject identification

Subject identification numbers will be assigned sequentially to the subjects who have consented to participate in the study, according to the range of subject identification numbers allocated to the center.

6.2.2. Randomization of treatment

6.2.2.1. Randomization of supplies

The list of treatment numbers for the supplies is generated at GSK Biologicals, using MATerial EXcellence (MATEX), a program developed for use in Statistical Analysis System (SAS) (Cary, NC, USA) by GSK Biologicals.

6.2.2.2. Treatment allocation to the subject

The treatment numbers will be allocated by dose.

6.2.2.2.1. Study group and treatment number allocation

The target is to enroll approximately 150 subjects (26 subjects per vaccine group and between 20 and 30 subjects in the infectivity control group). Randomization will be performed on the investigational vaccine groups (AduFx, 2PedFx, PedFx, Adu2Fx, and Adu1Fx) and not for the infectivity controls. The first enrolled 130 subjects will be allocated to the vaccine groups (AduFx, 2PedFx, PedFx, Adu2Fx, and Adu1Fx) and the subsequent subjects will be allocated to the infectivity controls group.

Allocation of the subject to a study group at the investigator site will be performed using a randomization system on internet (SBIR). The randomization algorithm will use a minimization procedure accounting for center.

After obtaining the signed and dated ICF from the subject and having checked the eligibility of the subject, the site staff in charge of the vaccine administration will access SBIR. Upon providing the subject identification number, the randomization system will determine the study group and will provide the treatment number to be used for the first dose.

The number of each administered treatment must be recorded in the eCRF on the Vaccine Administration screen.

When SBIR is not available, please refer to the SBIR user guide or the Study Procedures Manual (SPM) for specific instructions.

6.2.2.2.2. Treatment number allocation for subsequent doses

For each dose subsequent to the first dose, the study staff in charge of the vaccine administration will access SBIR, provide the subject identification number, and the system will provide a treatment number consistent with the allocated study group.

The number of each administered treatment must be recorded in the eCRF on the Vaccine Administration screen.

6.3. Method of blinding

This study is open label.

The laboratory in charge of the laboratory testing will be blinded to the treatment, and codes will be used to link the subject and study (without any link to the treatment attributed to the subject) to each sample.

6.4. General study aspects

Supplementary study conduct information not mandated to be present in this protocol is provided in the accompanying SPM. The SPM provides the investigator and the site personnel with administrative and detailed technical information that does not impact the safety of the subjects.

6.4.1. Mosquito challenge

Subjects from the five vaccine groups (AduFx, 2PedFx, PedFx, Adu2Fx, and Adu1Fx) completing their immunization course will be challenged with sporozoite-infected mosquitoes to determine whether the expected protective response has developed. Such challenges are mandated by the absence of any laboratory tests that will unequivocally predict protection. The challenge is scheduled to occur approximately 90 days (three months) after the last vaccination (Day 286 [Visit 11]).

Unimmunized infectivity control subjects will also be challenged to verify the adequacy of the challenge.

Subjects undergoing malaria challenge will receive an emergency notification card that outlines their participation in the study with details on the exposure to malaria, as well as the appropriate investigator contact telephone numbers. Details of this information may vary, depending on the venue selected for the hotel phase of the study.

6.4.1.1. Contraindications to malaria challenge

The only absolute contraindication to mosquito challenge is pregnancy. If this occurs after immunization but before undergoing challenge, the subject must not be challenged and she will be followed for the duration of the study or pregnancy whichever is longer.

A subject with a minor illness but who does not have fever during the pre-challenge assessment may be challenged at the discretion of the investigator. If the subject is moderately to severely ill with fever on the day of the challenge, he/she will not be challenged. Challenge can be performed within the time window defined in [Table 9](#), [Table 10](#) and [Table 11](#), at the discretion of the investigator if the subject becomes well. Subjects who will not be challenged will be followed for the duration of the study.

Any conditions which according to the judgment of the investigator would make the challenge unsafe.

6.4.1.2. Parasite and mosquito strains

The 3D7 clone of *P. falciparum* is a human malaria isolate that has never been passed through monkeys, is well adapted to culture, is a good producer of gametocytes that can infect mosquitoes, is susceptible to currently available, approved, anti-malarial compounds, and has previously been used in the Walter Reed Army Institute of Research (WRAIR) challenge model to successfully infect human subjects under a Biologics Master File submitted to the Food and Drug Administration (FDA). Master seed lots of these parasites have been developed and stored at WRAIR. All blood products used for malaria and mosquito culturing will be commercially tested for HIV, HBsAg, HCV, and syphilis. The mosquitoes used will be laboratory-born and reared *Anopheles stephensi*.

6.4.1.3. Infection of human subjects

Mosquitoes infected approximately 2-3 weeks earlier that are likely to contain sporozoites in their salivary glands will be allowed to feed on the subjects. For each subject, five mosquitoes will be allowed to feed over five minutes, after which they will be dissected to confirm how many were infected, and the salivary glands scored. If required, additional mosquitoes will be allowed to feed until a total of five infected mosquitoes with a minimum 2+ salivary glands score have fed [Wirtz, 1987]. The mosquito feedings will be performed in a secure insectary of the Department of entomology at WRAIR. Subjects will be observed for at least 30 minutes following completion of the sporozoite challenge in order to assess them for any evidence of acute allergic reactions related to mosquito exposure. To date, no severe allergic reactions related to mosquito bites have been documented in the context of the WRAIR malaria challenge model. Routinely, transient local allergic reactions (itching, rash) typical of mosquito bites occur at sites of the bites.

6.4.1.4. Determining parasitemia

Post-challenge, parasitemia will be determined by microscopy of Giemsa-stained thick blood films (smear). Microscopy will be performed on thick smears using a validated standard operation procedure.

All blood films (positive and negative) will be archived at the study centers for later re-examination and confirmation, if required.

6.4.1.5. Management of infected human subjects

The pre-patent period for *P. falciparum* in man normally averages 9-12 days. In previous studies, the pre-patent period in controls varied from 7-18 days. The shortest reported pre-patent period in man is five days, and the longest is 25 days [Ballou, 1987]. An immunized individual who does not have complete protection may have a prolongation of the parasite pre-patent period.

Beginning on Day 5 (Day 291 [Visit 12]) after their challenge, subjects will be seen and evaluated daily by a study investigator and blood will be drawn for blood smears to check for the presence of parasites as described in Section 6.4.1.4. If fever or symptoms develop at any time, blood smears will be done more frequently (every 6 to 12 hours), and a study investigator will evaluate the subject. A confirmed positive result will be relayed immediately to the on-call investigator/study personnel by the microscopists. The infection will be treated early (i.e. as soon as parasites can be identified on thick smear) according to the treatment regimen outlined in Section 6.4.1.6.

Beginning on Day 9 post-challenge (Day 295 [Visit 16]), a group of hotel rooms in the local area of WRAIR, will be reserved for malaria-challenged subjects. The subjects will be required to spend their nights there to allow for more rapid assessment of any potential symptoms of malaria during the hours that the study centers are closed. There will be an investigator present on-site and available for subject assessment. There will also be qualified study personnel on site 24 hours per day during the hotel phase of the study.

A blood sample for assessment of parasitemia (PCR testing) will be collected on the day of subject entry into the hotel phase (Day 295 [Visit 16]) to provide the study team an estimate of the number of subjects likely to develop malaria within the first few days of the hotel phase. This will allow the principal investigator and the study team to maximize subject safety by properly allocating resources and medical personnel to meet any high demand periods (i.e. periods when a large number of subjects are/will become ill). These samples will be processed by and assessed at WRAIR.

During the hotel phase, all challenged subjects will be assessed on a daily basis in an identical manner. An evaluation will be done each morning (headache, muscle aches, etc.) and blood will be drawn for smear. All challenged subjects will be instructed to check in with clinical staff by telephone call or in-person each evening during the hotel stay until they are positive for malaria. They will be asked if they feel any differently since they were seen in the morning. At any time required, the on-duty investigator will arrange for the timely production of blood smears, along with their examination and interpretation, in order to treat rapidly those subjects in whom therapy for malaria is indicated. Once a positive smear is identified, daily blood films will continue to be obtained until three consecutive films are negative (separated by more than 12 hours). A complete blood count and serum chemistry tests will be done when parasites are initially found in the blood (this could be done on the day of parasitemia detection or the day after).

The maximum hotel stay for malaria-challenged subjects should be approximately 10 days (Day 295 [Visit 16] to Day 304 [Visit 25]). A subject who develops malaria, is treated, and has three consecutive negative malaria smears (separated by more than 12 hours), will not need to remain in the hotel. The investigators will be responsible for accounting for any subjects who do not arrive in the hotel during the challenge phase. If required, the investigators will physically locate and treat any malaria-infected subject who is unable to maintain the follow-up dictated by this study.

If infection does not develop within 18 days, the subject will be released from staying nightly at the hotel. Subjects who do not develop malaria will be required to come to the clinical center for evaluation and blood drawing for smears every two days up to 28 days post-challenge (Days 306 [Visit 26], 308 [Visit 27], 310 [Visit 28], 312 [Visit 29], and 314 [Visit 30]). A subject who develops malaria and has three consecutive (separated by more than 12 hours) negative smears following initial treatment may be excused from the remaining hotel visits and the late post-challenge clinic visits at Days 306, 308, 310, and 312 (20, 22, 24 and 26 days post-challenge), but will be required to come to the clinic center at Day 314 (28 days post-challenge [Visit 30]). Telephone contact will be made if the subject does not keep a scheduled follow-up appointment. Symptom screening via telephone may suffice in lieu of clinical visits for Days 306, 308, 310, or 312 which fall upon a weekend.

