 - Blood sample for assessment of parasitemia (PCR testing) will be collected on the day of subject entry into the hotel phase (Day 295 [Visit 16]) to provide an estimate of the number of subjects likely to develop malaria within the first few days of the hotel phase.
 - Blood sample for assessment of parasitemia (blood smear) will be collected daily for 14 days (from Day 291 [Visit 12] to Day 304 [Visit 25]) and then every two days for nine days (Day 306 [Visit 26], Day 308 [Visit 27], Day 310 [Visit 28], Day 312 [Visit 29], and Day 314 [Visit 30]). For subjects who develop malaria, blood smear may be discontinued once the subject has three consecutive negative smears (separated by more than 12 hours) following the initial treatment (see Section 6.4.1).
 - Blood samples for testing of HIV, hepatitis C virus (HCV) and HBsAg will be collected from all subjects at screening.
 - Urinary pregnancy test (urine beta-human chorionic gonadotropin [β -HCG]) will be performed on all women at screening, before each vaccine dose for vaccinated subjects and on the day of challenge.
- Type of study: self-contained.
 - Data collection: electronic Case Report Form (eCRF).

- Safety monitoring:
 - Each subject will be observed for at least 30 minutes after vaccination to evaluate and treat any acute AEs.
 - Each subject will be observed for at least 30 minutes following completion of the sporozoite challenge to evaluate and treat any acute allergic reactions.
 - All SAEs (all, fatal, related to the investigational vaccine) and pregnancies will be reported until study end (Day 376).
 - All AEs and SAEs leading to withdrawal from further vaccination will be reported until study end (Day 376) for all vaccinated subjects (AduFx, 2PedFx, PedFx, Adu2Fx, and Adu1Fx groups).
 - Meningitis and pIMDs are AEs of specific interest to be reported until study end (Day 376; see Section 9.1.5) for all vaccinated subjects (AduFx, 2PedFx, PedFx, Adu2Fx, and Adu1Fx groups).
 - Solicited local and general AEs will be collected from all vaccinated subjects (AduFx, 2PedFx, PedFx, Adu2Fx, and Adu1Fx groups) during seven days (day of vaccination and six subsequent days) after each dose of study vaccine.
 - Unsolicited AEs will be collected from all vaccinated subjects (AduFx, 2PedFx, PedFx, Adu2Fx, and Adu1Fx groups) during 30 days (day of vaccination and 29 subsequent days) after each dose of study vaccine.

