Record any intercurrent medical conditions	•	•	•	•	•	•	•	•	•	•	•	•		•	•
Distribution of diary cards		0	0				0								
Return of diary cards			0			0				0					
Diary card transcription by investigator			•			•				•					
Recording of solicited local and general AEs (Days 0–6) post-vaccination		•	•				•								
Recording of unsolicited AEs (Day 0-29) post-vaccination		•	•	•	•	•	•	•	•						
Recording of AEs (Day 0-29) post-challenge											•	•	•	•	
Recording of SAEs (all, fatal, related) and pregnancies		•	•	•	•	•	•	•	•	•	•	•	•	•	•
Recording of SAEs related to study participation, or to a concurrent GSK medication/vaccine	•	•	•	•	•	•	•	•	•	•	•	•	•	•	•
Recording of all AEs and SAEs leading to withdrawal from further vaccination		•	•	•	•	•	•	•	•	•	•	•	•	•	•
Recording of AEs of specific interest ^f		•	•	•	•	•	•	•	•	•	•	•	•	•	•
Study Conclusion															•

β-HCG: Beta-human chorionic gonadotropin; PBMC: peripheral blood mononuclear cells; Vacc: vaccination.

* Visit 12 = 291, Visit 13 = Day 292, Visit 14 = Day 293, Visit 15 = Day 294, Visit 16 = Day 295, Visit 17 = Day 296, Visit 18 = Day 297, Visit 19 = Day 298, Visit 20 = Day 299, Visit 21 = Day 300, Visit 22 = Day 301, Visit 23 = Day 302, Visit 24 = Day 303, Visit 25 = Day 304, Visit 26 = Day 306, Visit 27 = Day 308, Visit 28 = Day 310, Visit 29 = Day 312.

** A blood sample for biochemistry and hematology parameters will be collected the day of first parasitemia (between Visit 12 [Day 291] and Visit 29 [Day 312]).

*** Blood sample for assessment of parasitemia (blood smear) will be collected daily for 14 days (from Day 291 [Visit 12] to Day 304 [Visit 25]) and then every two days for nine days (Day 306 [Visit 26], Day 308 [Visit 27], Day 310 [Visit 28], Day 312 [Visit 29], and Day 314 [Visit 30]). For subjects who develop malaria, blood smear may be discontinued once the subject has three consecutive negative smears (separated by more than 12 hours) following initial treatment.

CONFIDENTIAL

205081 (MALARIA-092)
Protocol Administrative Change 1 Final

**** Blood sample for assessment of parasitemia (PCR testing) will be collected on the day of subject entry into the hotel (Day 295).

a Including a check of NHANES I criteria and electrocardiogram (see [APPENDIX C](#)).

^b The screening laboratory results (HIV, HCV, HBsAg, ALT, AST, creatinine, hemoglobin, leukocytes [WBC], platelets, and urine β -HCG) must be checked during the screening activities and before randomization.

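### The weekend telephone option in Protocol 6.4.1.5 contradicts the late smear schedule and can widen the gap between slides from 2 to 4 days, blurring recorded onset of late infections

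*Protocol*

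**What the plan says.** Two rules cover the same four visits, study Days 306, 308, 310 and 312 (Visits 26 to 29).

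- **The smear rule.** Protocol 6.4.1.5 states: "Subjects who do not develop malaria will be required to come to the clinical center for evaluation and blood drawing for smears every two days", and lists Days 306 to 314. Section 3, the footnotes to Tables 6, 7 and 8, and Table 19 repeat this with no weekend exception. The Table 6 footnote begins "Blood sample for assessment of parasitemia (blood smear) will be collected daily for 14 days" and continues with alternate-day smears to Day 314. Section 3 also bars waivers other than for immediate safety concerns and makes the Section 6.5 procedures mandatory.
- **The telephone rule.** The last sentence of the same paragraph of 6.4.1.5 reads: "Symptom screening via telephone may suffice in lieu of clinical visits for Days 306, 308, 310, or 312 which fall upon a weekend". Day 314 is not on that list.

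Section 4 counts an infection only when parasites are "detected by blood slide reading". The only PCR sample is on Day 295. On late infection, 6.4.1.5 gives a control pre-patent range of 7 to 18 days, a longest reported value of 25 days, and adds: "An immunized individual who does not have complete protection may have a prolongation of the parasite pre-patent period".

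SAP 6.3.2.2 ends time at risk at the Day 314 visit and applies no censoring or elimination for incomplete follow-up in the proportion analysis. It has no rule for a skipped smear.

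**The concern.** A telephone call cannot produce a slide, so using the option removes a scheduled reading of the efficacy endpoint. A subject who was treated and has three negative smears is already excused from these visits by the same paragraph. The option therefore acts mainly on subjects who have not yet been diagnosed.

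On the protocol's own figures, few controls should still be undiagnosed after post-challenge day 18, whereas incompletely protected vaccinees may be. Any loss of late readings would thus fall mainly on the vaccine groups and affect the dating of late infections. The site also cannot tell whether a missing weekend slide is permitted or is a deviation, and the SAP does not say how to treat it.

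**Working it through.** **1. The schedule.** Post-challenge day = study day − 286. Daily smears run from 291 − 286 = 5 to 304 − 286 = 18, which is 14 smears. Days 306, 308, 310, 312 and 314 are post-challenge days 20, 22, 24, 26 and 28, which is 5 more. That gives 19 in all and matches the protocol's count.

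**2. Which visits fall on a weekend.** Number the challenge weekday w from Monday = 0 to Sunday = 6. Post-challenge day d falls on weekday (w + d) mod 7, and 5 or 6 means a weekend. The protocol does not fix the challenge weekday, so all seven are shown. The last two columns move Saturday to Friday and Sunday to Monday.

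| Challenge | Visits on a weekend | Widest gap if skipped | Smear days if moved | Widest gap if moved |
|---|---|---|---|---|
| Mon | 20 (Sun), 26 (Sat) | 4 (18–22, 24–28) | 18, 21, 22, 24, 25, 28 | 3 |
| Tue | 26 (Sun) | 4 (24–28) | 18, 20, 22, 24, 27, 28 | 3 |
| Wed | 24 (Sat) | 4 (22–26) | 18, 20, 22, 23, 26, 28 | 3 |
| Thu | 24 (Sun) | 4 (22–26) | 18, 20, 22, 25, 26, 28 | 3 |
| Fri | 22 (Sat) | 4 (20–24) | 18, 20, 21, 24, 26, 28 | 3 |
| Sat | 22 (Sun) | 4 (20–24) | 18, 20, 23, 24, 26, 28 | 3 |
| Sun | 20 (Sat) | 4 (18–22) | 18, 19, 22, 24, 26, 28 | 3 |

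No challenge weekday avoids a weekend visit. With full use of the option, 18 of 19 scheduled smears remain (17 of 19 for Monday).

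**3. Effect on recorded onset.** Two skipped smears are never adjacent. An infection that the skipped slide would have shown is therefore found at the next smear, 2 days later, if that smear is taken on its day. For scale, take the design assumption of 6 infections in a group of 20 (Protocol 11.4). If one of the six is dated 2 days late, the mean onset in SAP Template 12 shifts by 2/6 = 0.33 day.

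**4. Log-rank test against controls.** Suppose every control is positive by day 18. A later vaccinee onset then occurs when only vaccinees are at risk. Observed equals expected, the variance term is zero, and moving the onset changes nothing.

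Suppose instead that one control is never infected (19/20, as in 11.4):

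- One late vaccinee: 15 vaccinees and 1 control are at risk. The contribution is 1 − 15/16 = 1/16, the same on day 20 or day 22.
- Two late vaccinees, on days 20 and 22: the contribution is 1/17 + 1/16 = 0.121. If the first is delayed to day 22, the tie gives 2 − 2 × 16/17 = 2/17 = 0.118. The difference is about 0.004 of an event.

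**5. Occurrence endpoint.** A case is lost only if no later slide is positive. The plan's own efficacy figure is 1 − (6/20)/(19/20) = 1 − 6/19 = 68.4%, against its stated value of approximately 68%. Purely as an illustration, losing 1 or 2 of the 6 would give 1 − 5/19 = 73.7% or 1 − 4/19 = 78.9%. Fisher's p is below 0.0001 in all three cases. The documents give no rate of late infection, so the true loss cannot be estimated and may be zero.

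**The case against.** The case against treating this as serious is strong, and most of it stands.

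- **The endpoint is still measured.** A reader might infer that parasitemia could go unmeasured. It could not: one or two of 19 readings may be skipped, all 14 daily smears remain, and the Day 314 smear is outside the option. One caution is that Tables 9 to 11 allow Visit 30 at 28 ± 7 days, so the last slide need not be on day 28.
- **The comparison with controls is not flattered.** It is tempting to say that late dating makes the vaccine look better in the time-to-onset test. Step 4 shows that it does not, because the log-rank statistic depends on the order of events and who is at risk, not on elapsed days.
- **No direction is shown against AduFx.** Both arms are vaccinated and share the same option.
- **Late breakthrough infection is possible, not predicted.** The protocol says that prolongation may occur and gives a usual average pre-patent period of 9 to 12 days.
- **Symptom reports do not become cases.** A reader might infer that an unblinded symptom report replaces a blinded slide reading. Only a slide makes a case, and under 6.4.1.5 symptoms at any time lead to smears every 6 to 12 hours. What can be missed is parasitemia without reported symptoms during a 4-day gap.
- **The figures are ceilings.** The option is permissive, and the table assumes that it is used every time.

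None of this removes the contradiction. A slide cannot be both required and replaceable by a call on the same day. Because some weekend visit is unavoidable, the conflict will arise for every undiagnosed subject.

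**Conclusion.** The point holds as an inconsistency with a modest effect on measurement. If the option is used, each subject undiagnosed at post-challenge day 18 loses one late slide (two for a Monday challenge), and the widest gap doubles from 2 to 4 days. Recorded onset of a late infection can be up to 2 days late. The outputs affected are the onset summaries, the Kaplan-Meier curves and the between-schedule comparisons with AduFx, with no predictable direction.

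The documents do not support a claim that the primary efficacy result is biased. An infection that stays patent and is sampled later is still counted. Only a subject with no later positive slide would be lost as a case, and that subject would remain in the denominator as uninfected under SAP 6.3.2.2.

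The 2-day figure assumes that the next smear is taken on its scheduled day. The weekday results need no assumption beyond the visit days themselves. The correction is worth making because it is cheap and the present text cannot be followed consistently.

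**What to change.** Reconcile Section 6.4.1.5 with Section 3, the footnotes to Tables 6 to 8 and Table 19. State that a telephone call may supplement an endpoint smear but does not replace it. Where Day 306, 308, 310 or 312 falls on a weekend, collect that smear on the adjacent weekday (Saturday to Friday, Sunday to Monday) and record its actual date. In SAP 6.3.2.2, state that time to onset uses the actual smear date, and say how a smear that is still missed will be handled and reported. This concerns endpoint sampling only; what clinical follow-up is adequate on those days is for the sponsor and investigators.

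The cost is one protocol sentence with matching table notes and one addition to the SAP. No extra samples are needed, and no weekend staffing, on the assumption that the clinic is open on weekdays. All four late smears are kept and the widest gap is 3 days. The downside is that some late smears fall one day off schedule, so the planned 2-day spacing is not fully restored.
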